## **I. Abstract**

Opioid medications are widely used after many orthopedic procedures and are routinely prescribed after shoulder replacement surgery. Despite the high prevalence of opioid abuse and misuse, there is no standardized mechanism for patients to dispose of unused opioid medications safely and securely and the average number of opioid pills required after shoulder replacement surgery is still unknown. In a prior pilot study conducted by our group (IRB# 202012142), we analyzed opioid consumption patterns of patients undergoing shoulder arthroplasty as well as their adherence to a safe and secure disposal mechanism for excess opioid pills. We achieved a 94% retention rate and preliminary results showed that most of the subjects were 60 years of age and older.

The objective of the current proposal is to: (1) develop pre-operative education materials related to post-operative opioid use following shoulder arthroplasty; (2) pilot the impact of this educational intervention; (3) examine the effect of providing disposal mechanisms for unused opioid pain medications following shoulder arthroplasty. Our proposal is to conduct a single blinded randomized controlled trial of patients undergoing total shoulder replacement, both anatomic total shoulder arthroplasty (TSA) and reverse shoulder arthroplasty (RSA) at UIHC. This randomized controlled trial will compare: (1) education plus opioid disposal to the standard of care (SC). We hypothesize that pre-operative opioid education modules combined with a structured opioid disposal program will decrease opioid consumption following shoulder arthroplasty.

## **II. Background and Significance/Preliminary Studies**

Opioid medications are involved in thousands of deaths in the United States annually (1), and the opioid crisis remains a major public health concern in the United States. Since 1999 overdose deaths involving opioids, including prescription opioids, heroin, and synthetic opioids, have increased significantly (2). Despite the opioid epidemic being declared a public health emergency by the Department of Health and Human Services (HHS) in 2017, there are still unmet needs and therefore strategies that provide durable solutions to the opioid crisis are critical.

According to data published by the Department of Health and Human Services, increased prescription of opioid medications led to widespread misuse of both prescription and non-prescription opioids (15). The number of overdoses and deaths from prescription opioids has increased since 1990 and correlates with a growth in the number of opioid prescriptions (3).

Opioid medications are commonly prescribed for orthopedic conditions. In addition to the risk of abuse, opioids carry a number of other health risks such as respiratory depression, confusion (5), and an increase in the risk of falls and fractures among seniors (16). The concern for opioid abuse and misuse is rising among the elderly population. An article published in the CDC's Morbidity and Mortality weekly report showed that during 2017-2018 even though opioid-related death rates decreased for persons aged 15-64, these rates actually increased among persons aged  $\geq 65$  years old (17). Furthermore, the HHS Office of Inspector

General released a report based on an analysis of prescription drug event records for Medicare Part D which revealed that in 2016 one out of every three beneficiaries received at least one opioid prescription (7).

The rate of shoulder arthroplasty has increased dramatically over the past 10 years (6, 12). Most patients undergoing shoulder arthroplasty are over the age of 60. In our pilot study we found that 81% of our subject population were >60 years of age. We believe that it is crucial to address opioid consumption patterns among this elderly population.

### **III. Study Aims**

AIM 1: Develop pre-operative opioid educational modules for patients undergoing shoulder arthroplasty.

AIM 2: Evaluate the impact of educational materials on opioid consumption following shoulder arthroplasty when compared to standard of care. Hypothesis: Pre-operative educational modules, developed by an interdisciplinary team, will prove to be successful in decreasing the amount opioid medication taken after shoulder arthroplasty.

AIM 3: Evaluate a structured and streamlined disposal protocol and its effect on opioid disposal rates. Hypothesis: By promoting and implementing a structured and secured opioid disposal mechanism, patients undergoing shoulder arthroplasty will more frequently dispose of excess opioid medications.

## **V. Study Design**

Experimental design: single-blinded randomized controlled trial of patients undergoing total shoulder arthroplasty.

The study will include male and female patients  $\geq$  18-years-old who have been indicated for total shoulder arthroplasty. The total number of subjects will be 136. Sample size determination and power analyses: A sample size estimate was performed based on previous literature and data from our pilot study that showed nearly 55% of subjects returned 10 or more out of 40 tablets. Assuming ~55% will return 10 or more out of 40 tablets in the control group, a total of 68 subjects per group (n=136 total, with calculated 10% drop out) would provide 80% power, with an alpha level of 0.05 (2-sided test), to detect a 25% difference in the proportion who return 10 or more tabs in the brochure/video intervention group (35%).

*a. Study outcomes/endpoints:*

AIM 1: Develop pre-operative opioid educational modules for patients undergoing shoulder arthroplasty.

AIM 2: Evaluate the impact of educational materials on opioid consumption following shoulder arthroplasty when compared to standard of care.

AIM 3: Evaluate a structured and streamlined disposal protocol and its effect on opioid disposal rates.

## **VI. Study Procedures**

Inclusion criteria: patients who are 18 years of age and older who are indicated for primary total shoulder arthroplasty (both anatomic and reverse) at the Shoulder Surgery clinic at UIHC. All patients will be English speaking and have the ability to provide informed consent for the study. Patients will be excluded if they are  $<18$  years old, non-English speaking, pregnant, unable to consent for themselves, revision shoulder arthroplasty, arthroplasty for proximal humerus fracture, patients with a history of chronic opioid

consumption or patients who have contraindications for opioid consumption.

The medical records will only be accessed by the investigators for the purpose of collecting data pertaining solely to the study at hand and only data necessary to answer the research questions will be collected from the subjects' medical records. The study will involve the same data we would have access to in the course of our professional relationship with the patient. This data will only be available to the primary investigator and to the research coordinator. Without access to protected health information we would be unable to assess inclusion/exclusion criteria and the variables in study. Only members of the research team will have access to the protected health information. All identifying paper documents will be kept in locked cabinets at the research coordinator's office. All electronic information will be kept in password protected files. Data will be collected using REDCap. Identifying information will be destroyed after all analysis has been completed and it is no longer needed.

Potential subjects will be approached in person during their usual visit to the Shoulder Surgery clinic. They will be provided a brochure with information about the research study. Discussion regarding the study and consent will be obtained in person in clinic.

During their preoperative work-up visit, at IRL and Main Hospital, patients will be invited to participate in the research study. The research coordinator will discuss the study with potential subjects in a private office or exam room. If the patient shows interest in participating, the research coordinator and the patient will go through the process of consent of participants. Potential subjects will be explained that the purpose of the study is to assess opioid consumption and disposal after shoulder replacement surgery, and that after their surgery, they will have to answer daily questionnaires about pain management and opioid consumption, that will be delivered through text message only during the first 2 weeks after surgery. Adequate time will be allotted to the patients in clinic to consider participating in the study. The study will require a waiver of an element of consent, in relation to the use of deception and blinding of subjects. Without the waiver of the element of consent our study results may be biased as subjects in the standard of care group may potentially change their behavior if they were aware of the information being concealed.

Patients will be screened according to inclusion and exclusion criteria at their indication visit for total shoulder arthroplasty. Participants will receive daily text messages with a link to a REDCap survey during the 2 weeks following the surgery. For participants who did not answer the daily surveys, or for the ones who are still taking opioid medications after 2 weeks, a survey will be available at clinic. Subjects will be able to answer the survey at their scheduled postoperative visits (standard of care). Participants will not have to attend any visits for research purposes only.

Patients will be randomized utilizing redcap. The randomization scheme will be performed in a 1:1 ratio.

After signing the informed consent, participants will be randomized into one of the 2 study arms (Arm 1: control/SOC, Arm 2: education and disposal).

Participants in Arm 1 will be the control group. These patients will undergo evaluation and treatment for total shoulder arthroplasty according to the current standard of care at the institution. This does not currently include any preoperative educational material regarding opioid consumption and/or disposal.

Participants in Arm 2 will receive at their preoperative work-up visit a brochure and will watch an educational video. Both educational materials (brochure and video) will address information about opioid medication, pain management techniques and how to properly dispose of any excess opioid medication after the surgery. In addition, participants in Arm 2 will receive an envelope in which they will be able to dispose their unused opioid pills. These envelopes will be the same ones used in our pilot study (IRB# 202012142). The disposal method consists of secured, labeled envelopes to dispose of the excess of Opioid medication. These envelopes will be provided by “Sharps Compliance, Inc.”, a company that manages pharmaceutical waste disposal programs for healthcare facilities. Through their “TakeAway Medication Recovery System Envelope (USPS)” they allow the collection and disposal of controlled substances (Schedules II-IV) and non-controlled medications. Subjects will be explained how to use the envelope and that since it is labeled they will not have to cover any charges.

Potential subjects will be explained that the purpose of the study is to assess opioid consumption and disposal after shoulder replacement surgery, and that after their surgery, they will have to answer daily questionnaires about pain management and opioid consumption, that will be delivered through text message only during the first 2 weeks after surgery. The questionnaires will be built using REDCap platform. Text messages will be sent using a platform built by the Mobile Technology Lab at UIHC.

Participants who did not answer the daily survey, or who continue taking opioid medications after 2 weeks following surgery, will have the opportunity to answer the survey at their postoperative visit at the Shoulder Clinic, using the clinic's tablets, either at their 2-week or 6-week postoperative visit.

Subjects lost to follow up will not be recontacted.  
Subjects will not receive monetary compensation.

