## ***IX. Data Analysis Plan***

The primary outcome measure is opioid consumption with and without pre-operative opioid education. By comparing the two arms we will determine the difference in opioid consumption between groups of patients who receive education and those who do not. We will also analyze opioid disposal in the two groups and compare disposal rates.

Descriptive statistics (means, medians, percentages, standard deviations, and interquartile ranges) for all variables will be computed overall and for each intervention group. The distributions of continuous variables will be evaluated for normality. If distributions are non-normal, continuous variables will be described as median (interquartile range) and compared across intervention groups using Wilcoxon-rank sum tests. Otherwise, continuous variables will be described as mean $\pm$ standard deviation and compared between intervention groups using independent t-tests. Categorical variables will be reported as frequencies(percentages) and compared between groups using the chi-square or exact test, as appropriate. To account for multiple comparisons between the three groups, p-values will be adjusted using the stepdown Bonferroni approach. We will utilize the chi-square test to determine whether there is a significantly greater proportion who (Hypothesis 1) return more than 10 tablets in Arm 2 versus Arm 1; and (Hypothesis 2) properly dispose of unused tablets in Arm 2 versus control Arm 1. If necessary, we will adjust for potential covariates using logistic regression in place of the chi-square test with the control group serving as the referent group.

A sample size estimate was performed based on previous literature and data from our pilot study that showed nearly 55% of subjects returned 10 or more out of 40 tablets.

Assuming ~55% will return 10 or more out of 40 tablets in the control group, a total of 68 subjects per group (n=136 total, with calculated 10% drop out) would provide 80% power, with an alpha level of 0.05 (2-sided test), to detect a 25% difference in the proportion who return 10 or more tabs in the brochure/video intervention group (35%).

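### After the two-week text period, no route is described for recording disposal in participants who answered the texts and stopped opioids by day 14, so ascertainment for Hypothesis 2 depends on post-randomisation opioid use

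*Combined protocol and SAP*

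**What the plan says.** Section VI (Study Procedures) sets the data collection. "Participants will receive daily text messages with a link to a REDCap survey during the 2 weeks following the surgery". Participants are told that "they will have to answer daily questionnaires about pain management and opioid consumption"; disposal is not named as a questionnaire topic.

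After the text period, a clinic survey is offered to two groups: those who left the daily surveys unanswered and, in the same sentence, "for the ones who are still taking opioid medications after 2 weeks, a survey will be available at clinic". Later in Section VI the same two groups are named again: "Participants who did not answer the daily survey, or who continue taking opioid medications after 2 weeks following surgery". They may answer "either at their 2-week or 6-week postoperative visit". The section also says: "Subjects lost to follow up will not be recontacted".

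The only other possible source of disposal data is the mail-back envelope. Section VI describes it for the intervention arm: "participants in Arm 2 will receive an envelope in which they will be able to dispose their unused opioid pills". It describes no count or tracking of returned envelopes, and no envelope for Arm 1.

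Section III (Aim 3) and Section IX (Data Analysis Plan) make disposal a comparison between arms. Hypothesis 2 is a chi-square test of the proportion who "properly dispose of unused tablets in Arm 2 versus control Arm 1". Section IX gives neither a time point nor a data source for it. The primary outcome in Section IX is opioid consumption.

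**The concern.** Leftover tablets are normally disposed of once a patient has finished with opioids. Participants who stop within two weeks are those most likely to have tablets left. If they have also answered their texts, they are the group for whom Section VI describes no later contact about disposal.

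The rule that decides who is asked again uses opioid use at two weeks. That is measured after randomisation, belongs to the primary outcome, and is what the education is meant to reduce. Two consequences follow if unrecorded late disposal is treated as no disposal. Both recorded rates fall, which costs power for Hypothesis 2. And if Arm 2 stops earlier, as the trial hypothesises, more of its late disposal goes unseen and the comparison is tilted against the intervention.

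**Working it through.** **Who is followed.** Crossing the two conditions in Section VI gives four groups:

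| Answered the texts? | Opioids at 2 weeks | Survey after the text period |
|---|---|---|
| No | Still taking | Yes, at the 2- or 6-week visit |
| No | Stopped | Yes, at the 2- or 6-week visit |
| Yes | Still taking | Yes, at the 2- or 6-week visit |
| Yes | Stopped | None described |

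Only the last group is left out. Early stoppers who did not answer the texts can still be surveyed.

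**Size.** The plan gives no figure on this point to reproduce, so what follows is an illustration. One input comes from the documents: 68 per group with 10% dropout, 68 × 0.9 = 61.2, or about 61 per arm. The rest are assumptions:

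- *u*, the share of an arm not asked after day 14: 70% (range 50-80%) in both arms, or 80% in Arm 2 and 60% in Arm 1;
- *l*, the share of disposal that occurs after day 14: 50% (range 25-75%), taken as the same for everyone;
- true disposal of 55% in Arm 2 and 30% in Arm 1, or 50% in both;
- unseen disposal is counted as none, and everyone who is asked gives a complete answer.

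Recorded rate = true rate × (1 − *u* × *l*).

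Power = Φ[(|d| − 1.96 × SE0) / SE1], where d is the difference between the two rates p1 and p2, p̄ is their mean, SE0 = √(2p̄(1 − p̄)/n), SE1 = √((p1(1 − p1) + p2(1 − p2))/n) and n = 61.

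*Full ascertainment, 55% vs 30%.* SE0 = 0.0895 and SE1 = 0.0866. (0.25 − 0.1754)/0.0866 = 0.861, so power is 80.5%.

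*Equal shares not asked.* 1 − 0.7 × 0.5 = 0.65. Recorded rates are 0.55 × 0.65 = 35.8% and 0.30 × 0.65 = 19.5%. The gap falls from 25 to 16 points. SE0 = 0.0810 and SE1 = 0.0796, so power is 51.9%. At the ends of the ranges:

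- *u* = 50%, *l* = 25%: 48.1% vs 26.3%, gap 22 points, power 71%;
- *u* = 80%, *l* = 75%: 22.0% vs 12.0%, gap 10 points, power 31%.

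*Unequal shares not asked (80% Arm 2, 60% Arm 1).* Recorded rates are 0.55 × 0.60 = 33.0% and 0.30 × 0.70 = 21.0%. The gap is 12 points and power is 31.9%. Power is 58% at *l* = 25% (44.0% vs 25.5%) and 12% at *l* = 75% (22.0% vs 16.5%).

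*No true difference, same unequal shares.* Recorded rates are 0.50 × 0.60 = 30% in Arm 2 and 0.50 × 0.70 = 35% in Arm 1, a false deficit of 5 points. Over *l* = 25-75% it runs from 0.5 × 0.20 × 0.25 = 2.5 to 0.5 × 0.20 × 0.75 = 7.5 points.

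*A different assumed split (70% Arm 2, 50% Arm 1, l = 50%).* An equal true 50% is recorded as 32.5% vs 37.5%, again a 5-point deficit. A true 55% vs 30% is recorded as 35.8% vs 22.5%, with power of 36%.

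**The case against.** **Other routes may exist.** A reader might infer that late disposal by these participants can never be recorded. The documents do not support that. Section V reports pilot data on numbers of tablets returned, and Section VI says the same envelopes are used again, so some way of counting returns may have existed. What stands is that the current plan describes none, and a count of envelopes would cover Arm 2 only and give the two arms different measurement methods.

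**The survey might be open to all.** Section VI goes on to say that subjects can complete the survey at routine postoperative visits, and that sentence names no restriction. But it follows directly on the restriction, and the section later repeats the two groups together with the visits. The restricted reading is the natural one. If the other was intended, the text should say so.

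**All early stoppers are lost.** This too might be inferred, and it is too broad: text non-responders who stopped early remain eligible for the clinic survey.

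**The more basic gap is the endpoint.** The questionnaires are not said to ask about disposal, those eligible may answer at two weeks rather than six, and Section IX gives Hypothesis 2 no source or time. This is correct, and the fix has to cover it. It does not remove the problem, because the eligibility rule in Section VI would still tie later ascertainment to opioid use.

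**The figures are assumed.** This stands in full. The 25-point gap equals the one in the tablet-return sample size but is not a disposal rate from the documents. Early stoppers have longer before day 14 to dispose of tablets, so their late share, and the loss, may be smaller. Leaving late disposal missing rather than counting it as none is not modelled, and the plan specifies neither. The false 5-point deficit would reach significance only about 8.5% of the time at 61 per arm.

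**Limited importance.** Disposal is not the primary outcome, and the trial is presented as groundwork for a larger study. Both are fair. A biased or attenuated disposal result would still be carried into that larger study.

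**Conclusion.** The concern holds for one defined group: participants who answered the texts and had stopped opioids by day 14. For them the plan describes no way to record later disposal, so ascertainment for Hypothesis 2 depends on a post-randomisation variable that the intervention is meant to change.

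The direction rests on two conditions. If unseen late disposal is counted as none, both recorded rates fall. If, in addition, Arm 2 stops earlier, the error works against Arm 2. A reader might infer a risk of a spurious benefit; under the trial's own hypothesis the error runs the other way, and the likelier harm is a missed or understated effect on disposal.

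The size is unknown. In the illustration, power of 81% falls to 52% (range 31-71%) when both arms are affected equally, and to about 32% (range 12-58%) with the 80/60 split. These figures show that the loss could matter; they do not estimate it. The point does not bear on the consumption comparison, which is the primary outcome.

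**What to change.** In Section VI, give the same questions to all randomised participants in both arms at the existing standard-of-care 6-week visit: how many tablets remain, how many were disposed of, and how. This applies whether or not they answered the texts or still take opioids. In Section IX, define Hypothesis 2 from that 6-week answer in both arms. With everyone asked, *u* = 0 and the recorded rate in the illustration equals the true rate.

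The cost is one short extra survey at a visit that already takes place, which keeps the commitment that nobody attends solely for research.

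A text-link fallback for those who miss the visit is optional and is not free. It would require amending the statements, including what participants are told, that texts are confined to the first two weeks, and the statement that subjects lost to follow-up are not contacted again.

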## ***VII. Privacy and Confidentiality Protections***

Only members of the research team will have access to the protected health information. All identifying paper documents will be kept in locked cabinets at the research coordinator's office. All electronic information will be kept in password protected files. Data will be collected using REDCap. Identifying information will be destroyed after all analysis has been completed and it is no longer needed.

